7.2. PARTICIPANT DISCONTINUATION/WITHDRAWAL FROM THE STUDY

Participants are free to withdraw from participation in the study at any time upon request, including post the 52-week double blind period of the study. The reason for participant discontinuation or withdrawal from the study will be recorded on the CRF.

8. STUDY ASSESSMENTS AND PROCEDURES

8.1. EFFICACY ASSESSMENTS

Clinical Assessments

All assessments will be performed at Oregon Medical Research Center, P.C. At screening, Week 0, Week 2, Week 4, and every visit thereafter until Week 100, the following will be done:

1. Physical examination (*complete exam at screening, baseline, Week 4, Week 16, and Week 52; targeted exam at every other visit per Investigator discretion)
2. Psoriasis Area and Severity (PASI)
3. Body Surface Area (BSA)
4. Static Physician's Global Assessment (sPGA)
5. DLQI (*at Weeks 0, 28, and 52 only)
6. Vital signs (temperature, blood pressure, heart rate, respiratory rate, and weight)
7. Past medical history, including past systemic treatments for psoriasis (*at screening visit only)
8. Columbia Suicide Severity Rating Scale (*at screening visit only)
9. Interim health history to assess for possible adverse events (*at all visits following the baseline visit)

Laboratory Assessments

At screening, Weeks 4, 8, 22, and 52, the following will be collected at Oregon Medical Research Center, P.C. and sent to a local laboratory:

1. Complete blood count (CBC) w/differential
2. Comprehensive metabolic panel
3. Urinalysis
4. Urine pregnancy test (*performed on-site only for women of child-bearing potential, at each visit up to Week 52, except Week 2)

At screening only, the following will be collected at Oregon Medical Research Center, P.C. and sent to a local laboratory:

1. HIV antibody
2. Hepatitis B panel
3. Hepatitis C antibody
4. Quantiferon Gold

At Weeks 0 and 52, the following will be collected at Oregon Medical Research Center, P.C. and shipped to the laboratory of [name] at the University of Michigan:

1. One 6 mm skin biopsy of lesional skin (at Weeks 0 and 52) and one 6 mm skin biopsy of peri-lesional skin (at Week 0); both will be bisected and processed as follows:
2. **Single cell sequencing and CyTOF imaging:** A 6 mm punch biopsy will be bisected with one half cryopreserved in CryoStor CS10 media (Millipore, Sigma) in a cryogenic vial, and the other formalin fixed for CyTOF imaging and IHC. The CryoStor CS10 media is an optimized preservation media, that is formulated to address the molecular and biological aspects of cells during the cryopreservation process thereby directly reducing the level of cryopreservation-induced delayed-onset cell death and improving post-thaw cell viability and function. Tissue will be stored at -80C until shipping and processing. At processing samples will be rapidly thawed in a water bath in a continuous agitation and placed onto 25mL of cold 1xHBSS (as described Guillaumet-Adkins A, Genome Biology, 45, 2017). Samples will be incubated in 0.4% dispase (Life Technologies) in Hank's Balanced Saline Solution for 30 minutes. Epidermis and dermis are then separated. Epidermis is digested in 0.25% Trypsin-EDTA (Gibco) with 10U/mL DNase I (Thermo Scientific) for 1 hour at 37 °C, quenched with FBS (Atlanta Biologicals), and strained through a 70 µM mesh. Dermis will be minced, digested in 0.2% Collagenase II (Life Technologies) and 0.2% Collagenase V (Sigma) in plain medium for 1.5 hours at 37°C, and strained through a 70µM mesh. Epidermal and dermal cells will be recombined, and libraries will be constructed by the University of Michigan Advanced Genomics Core on the 10X Chromium system. Libraries will then be sequenced on the Illumina NovaSeq 6000 sequencer to generate 151-bp paired end reads with a goal of 10,000 cells, each with approximately 10,000 reads per cell (100 million reads per sample). Data processing including quality control, read alignment, and gene quantification will be conducted using the 10X Cell Ranger software.
3. **Data Analysis:** Initial processing of the sequencing reads will be performed using 10X Genomics Cell Ranger software, which performs sample de-multiplexing, barcode processing, and single cell 5' gene counting. As recently summarized in an excellent review (Andrews TS, Mol Aspects Med 59, 114-122,2018), the key elements of scRNA-seq analysis include feature selection, dimensionality reduction, and clustering. Low quality reads and cells will be filtered by Seurat (Butler A, Nature Biotechnology 36, 411-420, 2018), and we will apply a scalable computational approach that utilizes the differences in expression values between cells shared across experiments to facilitate robust batch correction (Haghverdi L, Nature Biotechnology 36, 421-

427, 2018) and thus cell population (type) assignment. Data will be clustered using unique molecular identifier (UMI), and then each cell subpopulation will be analyzed, and characteristic gene expression determined. Furthermore, single-cell trajectory analyses (pseudotime) will be performed to quantify the state of individual cells. Our bioinformatic team will implement computational approaches to integrate single cell and bulk RNA-seq data.

4. **Bulk RNA-seq:** For RNA seq, RNA 151 nucleotide paired-end read will be performed using the NovaSeq platform, which generates >800 million reads per sequencing run. We will use barcode oligo adapters to allow multiplexing of 15 samples per lane and expect to generate >20 million uniquely mapped reads/sample on average (assuming >75% mapping rate). We will use our in-house analysis pipeline to perform adapter trimming and quality control procedures for the RNA-seq samples. Multiple testing correction will be used to identify statistically significant results (False Discovery Rate <10%). We will also conduct *in silico* analysis, including pathway, transcription factor, and co-expression analysis, to provide biological inference.
5. **CyTOF Imaging:** Formalin-fixed, paraffin-embedded tissue slides will be heated for 2 hours at 60°C, deparaffinized, and rehydrated. Slides will be placed in pH 9 Tris/EDTA antigen retrieval buffer and heated at 96°C for 30 minutes. After cooling, slides will be blocked in 3% BSA, and stained with a cocktail of metal-tagged antibodies overnight at 4 °C including CD45, E-Cadherin, CD4, CD8, collagen, and pan-actin, and TRM markers CD27 (Fluidigm #3171024D), CD127 (Fluidigm # 3168026D). These have already been optimized in a panel for staining at our labs. For staining for CD69, CD103, CD49a, and circulating memory markers: CD62L, CCR7, we will optimize those using Imaging Mass Cytometry Staining Protocol for FFPE sections. The stained tissue is ablated, and raw data acquired on the Hyperion Imaging System (Fluidigm).
6. **Imaging CyTOF Data Analysis:** Multiplexed imaging CyTOF data will be pre-processed using commercial acquisition software (Fluidigm) and converted to .TIFF images. These images will be segmented into individual cells using CellProfiler v3.1.8 for single-cell analysis. The t-SNE dimensionality reduction algorithm and the Phenograph unsupervised clustering algorithm will be performed on TRM markers (CD4, CD8, CD69, CD103, CD49a, CD62L, CCR7) using HistoCAT v1.75 software. For t-SNE and PhenoGraph, the data will be normalized to the 99th percentile. The Heatmap will be generated to show z-scored mean marker expression of each cluster. P values will be computed using 2-tailed Student's t tests assuming homoscedasticity.

Remaining tissue samples will be stored at the University of Michigan laboratory until the end of trial or until arrangement for shipping to AbbVie is made. Patient ICF will include language for future use of remaining tissue samples by AbbVie in additional research.

8.2. SAFETY AND OTHER ASSESSMENTS

The Principal Investigator (PI) shall comply with applicable Laws pertaining to reporting of Adverse Events to the competent regulatory authorities. In addition, the PI shall comply with the reporting requirements that are specified for each event listed below:

Event:	Report to AbbVie within:
Serious Adverse Events	four (4) calendar days if reporting a death or life-threatening event, and within eight (8) calendar days for all other Serious Adverse Events

Adverse Events	fifteen (15) calendar days
Safety Signals	fifteen (15) calendar days
Negative outcomes or untoward events during the course of a Study subject's pregnancy or upon delivery	fifteen (15) calendar days
Pregnancies experienced by a Study subject or a partner of a Study subject receiving an AbbVie product	fifteen (15) calendar days
Special Situations	fifteen (15) calendar days

The PI or designee shall promptly make available to AbbVie such records as may be necessary and pertinent to investigate any Safety Information, if specifically requested by AbbVie. AbbVie's contact for reporting Serious Adverse Events, Adverse Events, pregnancies, pregnancy experiences, Safety Signals and Special Situations is [contact].

"Product Complaint" means any suspected quality defect in an AbbVie product or its AbbVie-provided packaging, labeling or medical device component. Product Complaints may include, but are not limited to:

1. damaged or broken product or packaging issues
2. product appearance whose color/markings do not match the labeling
3. labeling discrepancies/inadequacies in the labeling/instructions
4. missing components/product
5. any death of a patient
6. device not working properly or use errors
7. any illness, injury, or adverse event in the proximity of the device
8. an adverse event that could be a result of using the device
9. any event needing medical or surgical intervention, including hospitalization, while using the device

In order for AbbVie to comply with all FDA requirements pursuant to 21 CFR 211 and 21 CFR 820, the PI or designee shall report to AbbVie within one (1) working day any Product Complaint. The PI or designee will report Product Complaints that involve an AbbVie product, whether AbbVie has supplied the AbbVie product used in the Study or not. AbbVie's contact for reporting Product Complaints is [contact].

8.3. ADVERSE EVENTS AND SERIOUS ADVERSE EVENTS

An adverse event (AE) is defined as any untoward medical occurrence in a patient, which does not necessarily have a causal relationship with their treatment. An adverse event can therefore be any unfavorable and unintended sign (including an abnormal laboratory finding), symptom, or disease temporally associated with the use of a medicinal product, whether or not the event is considered causally related to the use of the product.

Such an event can result from use of the drug as stipulated in the labeling, as well as from "special situations" as accidental or intentional overdose, medication error, occupational or accidental exposure, off-label use, drug abuse, drug misuse, lack of efficacy, or drug withdrawal, all which must be reported whether associated with an adverse event or not.

If an adverse event meets any of the following criteria, it is considered a serious adverse event (SAE):

Death of Patient:	An event that results in the death of a patient.
Life-Threatening:	An event that, in the opinion of the investigator, would have resulted in immediate fatality if medical intervention had not been taken. This does not include an event that would have been fatal if it had occurred in a more severe form.
Hospitalization:	An event that results in an admission to the hospital for any length of time. This does not include an emergency room visit or admission to an outpatient facility.
Prolongation of Hospitalization:	An event that occurs while the study patient is hospitalized and prolongs the patient's hospital stay.
Congenital Anomaly:	An anomaly detected at or after birth, or any anomaly that results in fetal loss.
Persistent or Significant Disability/Incapacity:	An event that results in a condition that substantially interferes with the activities of daily living of a study patient. Disability is not intended to include experiences of relatively minor medical significance such as headache, nausea, vomiting, diarrhea, influenza, and accidental trauma (e.g., sprained ankle).
Important Medical Event Requiring Medical or Surgical Intervention to Prevent Serious Outcome:	An important medical event that may not be immediately life-threatening or result in death or hospitalization but based on medical judgment may jeopardize the patient and may require medical or surgical intervention to prevent any of the outcomes listed above (i.e., death of patient, life threatening, hospitalization, prolongation of hospitalization, congenital anomaly, or persistent or significant disability/incapacity). Additionally, any elective or spontaneous abortion or stillbirth is considered an important medical event, and suspected transmission of an infectious agent via a medicinal product if no other serious criterion is applicable. Examples of such events include allergic bronchospasm requiring intensive treatment in an emergency room or at home, blood dyscrasias or convulsions that do not result in inpatient hospitalization, or the development of drug dependency or drug abuse.

The following definitions will be used to rate the severity for any adverse event being collected as an outcome/data point in the study and for all serious adverse events.

Mild:	The adverse event is transient and easily tolerated by the patient.
Moderate:	The adverse event causes the patient discomfort and interrupts the patient's usual activities.
Severe:	The adverse event causes considerable interference with the patient's usual activities and may be incapacitating or life threatening.

The following definitions will be used to assess the relationship of the adverse event to the use of product:

Reasonable Possibility	After consideration of factors including timing of the event, biologic plausibility, clinical judgment, and potential alternative causes, there is sufficient evidence (information) to suggest a causal relationship.
No Reasonable Possibility	After consideration of factors including timing of the event, biologic plausibility, clinical judgment, and potential alternative causes, there is insufficient evidence (information) to suggest a causal relationship

If no reasonable possibility of being related to product is given, an alternate etiology must be provided for the adverse event.

9. STATISTICAL CONSIDERATIONS

9.1. STATISTICAL HYPOTHESES

The study is exploratory in nature and is not statistically powered to detect differences between the treatment arms. All analyses will be descriptive with the goal of developing hypothesis-generating data. The statistical analyses will be performed by AbbVie data and statistical sciences (DSS). Complete and specific details of the statistical analysis will be described and fully documented in the Statistical Analysis Plan (SAP). The statistical analyses will be performed using SAS (SAS Institute Inc., Cary, North Carolina, USA).

9.2. SAMPLE SIZE DETERMINATION

The study is exploratory in nature and is not statistically powered for hypothesis testing. The sample size of 20 subjects is determined based on study feasibility.

9.3. ANALYSIS SET

The Full Analysis Set (FAS) includes all randomized subjects who received at least 1 dose of study drug. The FAS will be used for all efficacy and Baseline analyses. Subjects will be grouped according to treatment as randomized.

The Safety Analysis Set consists of all subjects who received at least 1 dose of study drug. For the Safety Analysis Set, subjects are assigned to a treatment group based on the treatment actually received, regardless of the treatment randomized.

9.4. HANDLING OF POTENTIAL INTERCURRENT EVENTS

There will be two major types of intercurrent events (ICE) in this study: risankizumab discontinuation due to lack of efficacy or intolerance, and risankizumab discontinuation due to other reasons. Each intercurrent event will be addressed by different strategies, specifically:

Table ** Handling of Potential Intercurrent Events

Intercurrent Event	Strategy	Description
risankizumab or study discontinuation due to lack of efficacy or intolerance	Composite variable strategy	Data after risankizumab or study discontinuation due to lack of efficacy or intolerance will be set to non-responder for binary endpoints. For continuous endpoints, set to last observation before discontinuation.
risankizumab discontinuation due to other reasons	Treatment policy strategy	Data after risankizumab discontinuation due to other reasons will be used regardless of whether the intercurrent event occurs.

9.5. METHODS FOR ANALYSIS OF DEMOGRAPHICS AND BASELINE CHARACTERISTICS

Demographics and baseline disease characteristics will be presented by descriptive statistics by treatment arm for the FAS. Medical history, prior therapy and medication, and concomitant medications will be summarized as well. Categorical variables will be summarized with frequency and percentage; percentages will be calculated with non-missing observations. Continuous variables will be summarized with descriptive statistics (number of non-missing observations, mean and standard deviation, median, minimum, and maximum).

9.6. METHODS FOR ANALYSIS OF PRIMARY OUTCOMES

For the primary outcomes, after handling of intercurrent events as specified in Section 9.4, the change from baseline in the number and/or effector function of epidermal CD8+CD103+ Trm cells at Week 52 will be summarized with mean, standard deviation, 95% confidence interval, and compared between the two treatment arms with t-test. Additional analysis with non-parametric test (e.g., Wilcoxon signed-rank test) will be performed, as appropriate. Details will be provided in the SAP.

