1. PROTOCOL SUMMARY

1.1. SYNOPSIS

Title: “Decreasing resident memory T cells while increasing clinical durability: higher induction doses of risankizumab for moderate-to-severe plaque psoriasis (KNOCKOUT)”

Study Description: This is a pilot study that explores whether higher induction doses of risankizumab (2x and 4x standard induction doses) can more effectively target resident memory (Trm) cells within psoriatic lesions, and whether more profound knock-down of Trm is associated with higher levels of complete clearance (i.e., PASI 100) and for longer periods of time.

Objectives: **Primary Objective:** to determine whether the reduction in the number and/or effector function of epidermal CD8+CD103+ Trm cells at Week 52 (compared to baseline numbers) in psoriasis patients treated with 4X standard induction doses of risankizumab (600 mg at Weeks 0, 4, and 16) is greater when compared to psoriasis patients treated with 2X standard induction doses of risankizumab (300 mg at Weeks 0, 4, and 16).

Secondary Objectives:

- 1) to compare the percentage of patients with PASI 100 (complete clearance) at Weeks 28, 40, 52 and 100 in patients receiving 4X standard induction doses of risankizumab vs. those receiving 2X standard induction doses of risankizumab and
- 2) to compare safety events over 100 weeks in patients receiving 4X standard induction doses of risankizumab vs. those receiving 2X standard induction doses of risankizumab

[figure not shown]

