3. OBJECTIVES AND ENDPOINTS

OBJECTIVES	ENDPOINTS	JUSTIFICATION FOR ENDPOINTS

Primary Objective: to determine whether the reduction in the number and/or effector function of epidermal CD8+CD103+ Trm cells at Week 52 (compared to baseline numbers) in psoriasis patients treated with 4X standard induction doses of risankizumab (600 mg at Weeks 0, 4, and 16) is greater when compared to psoriasis patients treated with 2X standard induction doses of risankizumab (300 mg at Weeks 0, 4, and 16).
	
Primary Endpoint: change from baseline in number and/or effector function of epidermal CD8+CD103+ Trm cells at Week 52 in psoriasis patients treated with 4X standard induction doses of risankizumab (600 mg at Weeks 0, 4, and 16) or 2X standard induction doses of risankizumab (300 mg at Weeks 0, 4, and 16).
	
Trm cells are the primary cells within psoriatic lesions (and healed skin) that are responsible for psoriasis recurrences after skin lesions have cleared. Targeting these cells, as proposed here, may lead to prolonged remission of psoriasis.

Secondary Objectives:
 
 1) to compare the percentage of patients with PASI 100 (complete clearance) at Weeks 28, 40, 52, and 100 in patients receiving 4X standard induction doses of risankizumab vs. those receiving 2X standard induction doses of risankizumab and 2) to compare safety events over 100 weeks in patients receiving 4X standard induction doses of risankizumab vs. those receiving 2X standard induction doses of risankizumab. 	
Secondary Endpoints:
 
 1) PASI 100 (complete clearance) response at Weeks 28, 40, 52, and 100 in patients receiving 4X standard induction doses of risankizumab or those receiving 2X standard induction doses of risankizumab and 2) safety events over 100 weeks in patients receiving 4X standard induction doses of risankizumab or those receiving 2X standard induction doses of risankizumab. 	
These are standard measures of efficacy and safety for psoriasis studies.

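### Section 9.6 compares change in Trm number by an unadjusted t-test with no stated scale; with 10 per arm, chance baseline imbalance can make the estimate imprecise

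*Combined protocol and SAP*

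**What the plan says.** Section 3 gives the primary endpoint as "change from baseline in number and/or effector function of epidermal CD8+CD103+ Trm cells at Week 52" in the two dose arms. Section 9.6 states that the "change from baseline in the number and/or effector function of epidermal CD8+CD103+ Trm cells at Week 52 will be summarized with mean", standard deviation and 95% confidence interval, and has it "compared between the two treatment arms with t-test". It then adds: "Additional analysis with non-parametric test (e.g., Wilcoxon signed-rank test) will be performed, as appropriate". It closes with "Details will be provided in the SAP".

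No log, ratio or percent-change scale is named, and no baseline covariate. ANCOVA and least-squares means appear only in the abbreviation list (Section 10.2). The document supplied contains no further SAP text that settles either choice.

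The Synopsis describes the study as exploring "whether more profound knock-down of Trm is associated with higher levels of complete clearance", and Sections 2.1 and 4.2 repeat the idea. Knock-down is nowhere defined as an absolute or a proportional quantity.

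Twenty patients are randomised 1:1 (Section 6.1.2), with no stratification stated. Eligibility sets lower limits for BSA and PASI and no upper limit (Section 5.1). Sections 9.1 and 9.2 call the study exploratory, unpowered and sized by feasibility.

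**The concern.** If the drug removes a fraction of the Trm cells present, a patient's fall in count is roughly baseline multiplied by that fraction. An arm that happens to start with fewer cells then shows a smaller average fall even when a larger share of its cells has gone. With 10 patients per arm and no baseline term in the comparison, such imbalance passes straight into the estimate.

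The non-parametric back-up does not help. Ranking the changes leaves them on the same scale, and the signed-rank test offered as the example is a paired test, so it does not compare the arms.

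At stake is the main product of a hypothesis-generating study: the direction and rough size of the dose contrast in Trm number.

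**Working it through.** **Plan's own figure.** There is no power calculation to reproduce; 20 is a feasibility number. From the documents: 10 per arm, change from baseline, unadjusted t-test. Two-sided 0.05 is assumed, because Section 9.6 states no level.

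**Step 1: can the direction reverse?** Suppose 4X falls from 50 to 10 cells and 2X from 100 to 40.
- Proportional reduction: 40/50 = 80% against 60/100 = 60%, favouring 4X.
- Raw change: −40 against −60, favouring 2X.

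The baselines here are deliberately unequal. How often chance produces this depends on baseline spread, which the documents do not give.

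**Step 2: rough size by hand.** Let baseline have mean M and coefficient of variation c, and let the arms lose fractions p4 and p2. Ignoring Week 52 noise:
- true difference in mean fall = (p4 − p2)·M
- standard error = c·M·√[(p4² + p2²)/10]
- chance of the wrong sign ≈ Φ(−difference/SE)

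For 15% v 30% remaining, p4 = 0.85 and p2 = 0.70. The difference is 0.15M and SE = c·M·√(1.2125/10) = 0.348·c·M. At c = 0.5, z = 0.15/0.174 = 0.86, giving about 19%. At c = 0.8, z = 0.15/0.279 = 0.54, giving about 30%.

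For 25% v 50% remaining, p4 = 0.75 and p2 = 0.50. The difference is 0.25M and SE = 0.285·c·M. At c = 0.5, z = 1.75, giving about 4%. At c = 0.8, z = 1.10, giving about 14%.

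**Step 3: simulation.** Assumptions: lognormal baseline, CV 50–80%, mean 20–100 cells with Poisson counting error; Week 52 = baseline × fraction remaining (15% v 30%, or 25% v 50%) × lognormal error with log-SD 0.6; no dropout. There were 20,000 trials per setting.

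| Analysis | Estimate favours wrong arm | Power |
|---|---|---|
| Raw change, t-test | 7–27% | 8–28% |
| Raw-scale ANCOVA | 2–5% | 30–48% |
| Log-scale ANCOVA, log(count + 0.5) | 1–5% | 36–60% |

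Matched setting by setting, the log scale adds about 4–17 points of power over raw-scale ANCOVA. At CV 30%, the wrong-arm rate for raw change is about 4–15%. A statistically significant result in the wrong direction occurs in under 0.5% of trials with a true effect.

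**Step 4: no true difference (30% remaining in both arms).** Raw change rejects in about 4–5% of trials. The log-scale analysis keeps about 5%, even with 7% zero counts at Week 52.

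**Step 5: a second set of assumptions.** With reductions of 80% v 60% and log-SD 0.6, raw change favours the wrong arm in 4%, 10%, 21% and 27% of trials at CV 0.3, 0.5, 1.0 and 1.5. Raw-scale ANCOVA gives 1–4% and log-scale ANCOVA about 0.6%. Power is 35%, 23%, 11% and 7% for raw change, against about 66% for log-scale ANCOVA. With a 70% reduction in both arms, raw-change type I error is 3.2–4.8%.

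**The case against.** Several points on the other side are sound.

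- **The plan does not contradict its own aim.** A reader might infer that knock-down means a proportional effect and that Section 9.6 therefore measures the wrong thing. The documents do not define the term, and the primary objective speaks of a reduction in number compared with baseline numbers, which fits an absolute change. The supportable criticism is that the scale is left open.
- **The simulations assume a multiplicative drug effect**, which favours the log scale by construction. No other mechanism was tested.
- **Most of the wrong-direction risk is not about scale.** A reader might see this as a scale problem separate from covariate adjustment. It is not: raw-scale ANCOVA alone brings the rate down to 2–5%, close to the 1–5% on the log scale.
- **The study is descriptive.** Section 9.1 disclaims power, Section 9.11 disclaims confirmatory testing, and no decision rule hangs on this t-test.
- **Details are deferred to the SAP**, so the gap may yet be closed there.

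What remains is that the only analysis set out for the primary outcome is unadjusted and has no stated relative scale. Being exploratory does not make an avoidably noisy estimate harmless, and the deferral identifies where the correction belongs.

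**Conclusion.** The concern holds as a loss of precision that is cheap to avoid. If the effect is proportional and baseline counts vary with a CV of 50–80%, the analysis as written gives a point estimate favouring the wrong arm in about 7–27% of trials and has power of about 8–28%. Baseline adjustment removes most of the directional risk. The log scale adds some power and reports depth of knock-down directly.

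A reader might go further and conclude that the primary result is biased, or that high-baseline patients will dominate it. Neither follows. Under randomisation the expected raw difference has the right sign, and type I error is not inflated. How far a few patients weigh on the mean depends on a baseline spread that the documents do not report; at CV 30% the wrong-arm rate falls to about 4–15%. The sizes given here rest on the assumed CV, cell counts, effect sizes and error SD. They concern cell number only, because effector function has no stated measure or scale.

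**What to change.** Before Trm results are compared by arm, state in Section 9.6 or the SAP:

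- **Main contrast for Trm number:** ANCOVA of log(Week 52 count + 0.5) on arm and log(baseline count + 0.5), reported as the ratio of geometric means, 4X over 2X, with 95% confidence interval. A ratio below 1 means fewer cells remaining on 4X for the same baseline.
- **Zero counts:** fix the 0.5 offset in advance and show the result with one alternative offset.
- **Supportive summary:** keep absolute change from baseline by arm.
- **Effector function:** give each measure its own stated scale, also with baseline as covariate.

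The cost is a few lines of SAP text and one model statement, using data already planned for collection. The downside is that the offset is arbitrary and matters more when counts are low, which is why a second offset should be shown.
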